3.2. Study Endpoints

The study objectives and corresponding endpoints are shown in the [Table 3.1.1](#).

3.3. Treatments

The dose selected in this study is the dose approved for the treatment of moderate to severe AD for Dupixent in US, EU, and all other countries that this study will be conducted.

Patients will receive either;

- Dupilumab 600 mg (2 x 300 mg dupilumab injections) on Day 1 (ie, the loading dose), followed by 1 dupilumab injection of 300 mg every two weeks (Q2W) until week 10, then 1 dupilumab + 1 placebo injection at Week 12 (to protect the blind while patients in placebo arm receive their loading dose), followed by 1 300 mg dupilumab injection Q2W with last injection at week 22 or
- Matching placebo for dupilumab (2 x 2mL placebo injections) on Day 1 (ie, the loading dose), then 1 placebo injection Q2W until week 10, and then 2 x 300 mg dupilumab injections at week 12 (ie, the loading dose), followed by dupilumab injections Q2W with last injection at week 22.

Non-investigational medical products

Starting on Day -7, all patients are required to undergo background treatment with medium-potency topical corticosteroids (TCS) [i.e., non-investigational medical products (NIMP)].

3.4. Dose Adjustment/Modifications

Dose modification of dupilumab for an individual patient is not allowed.

4. General Statistical Considerations

4.1. Sample Size

The sample size calculations were based on the subset of patients who reported ≥ 5 units of baseline sleep loss and ≥ 3 units of baseline pruritus scores on the SCORAD instrument in a previous study (AD1424) evaluating efficacy of dupilumab for AD.

Since no previous data are available on daily sleep on the NRS scale, the SCORAD sleep component (VAS) data was used as a basis for the sample size determination for the primary endpoint. The variability (standard deviation) estimate for the subset of patients mentioned above was 37% for the % change from baseline to week 12. Given the uncertainty in the variability from this variable to the NRS weekly average sleep score, the above variability was inflated by $\sim 20\%$, and assumed to be 44% for the primary sleep parameter. With these assumptions, a total sample of 150 (50 in placebo and 100 in dupilumab group) patients will provide 90% power ($\alpha = 0.05$, 2-sided) to detect a treatment difference of 25% (effect size, $\Delta/\sigma = 0.57$) for the percent change from baseline.

For secondary actigraphy endpoints, sample size estimates are provided in reference to Nemolizumab Ph2 data at week 4. For TST, to detect a 30 minutes difference between treatments: (2:1 allocation ratio; $\alpha=0.05$, 2-sided), assuming the same variability at week 16 weeks as seen for Nemolizumab at week 4 (=56 min), then 167 subjects are needed to provide 90% power. Furthermore, the proposed sample size would have $>90\%$ power to detect a difference of 10% for change from baseline in actigraphy based sleep efficiency, assuming a variability of 11% ($\alpha=0.05$, 2-sided). The variability estimate was based on for actigraphy based sleep efficiency at week 4, inflated by 50% to account for possible increase in variability over time (from week 4 to week 16). Of note, the data used for actigraphy parameters are limited.

Allowing for 20% dropouts, a total of approximately 201 patients will be enrolled in the study.

Considering the uncertainty of the variability of the primary endpoint, when data are available for this endpoint from about 50% of the patients completing Week 12, the variability will be assessed in a blinded manner, and the sample size will be re-estimated. If the re-estimated sample size is higher than the original estimate, the sample size may be increased accordingly, not to exceed a total of 150 additional patients.

Since this analysis will be performed in a blinded manner, no adjustment to the type I error will be made in the final analysis.

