9.2 SAMPLE SIZE DETERMINATION

The sample size calculations were based on the subset of patients who reported ≥ 5 units of baseline sleep loss and ≥ 3 units of baseline pruritus scores on the SCORAD instrument in a previous study (AD1424) evaluating efficacy of dupilumab for AD.

Since no previous data are available on daily sleep on the NRS scale, the SCORAD sleep component (VAS) data was used as a basis for the sample size determination for the primary endpoint. The variability (standard deviation) estimate for the subset of patients mentioned above was 37% for the % change from baseline to week 12. Given the uncertainty in the variability from this variable to the NRS weekly average sleep score, the above variability was inflated by ~20%, and assumed to be 44% for the primary sleep parameter. With these assumptions, a total sample of 150 (50 in placebo and 100 in dupilumab group) patients will provide 90% power (alpha = 0.05, 2-sided) to detect a treatment difference of 25% (effect size, $\Delta/\sigma = 0.57$) for the percent change from baseline.

For secondary actigraphy endpoints, sample size estimates are provided in reference to nemolizumab Ph2 data at week 4. For TST, to detect a 30 minutes difference between treatments: (2:1 allocation ratio; alpha=0.05, 2-sided), assuming the same variability at week 16 weeks as seen for nemolizumab at week 4 (=56 min), then 167 subjects are needed to provide 90% power. Furthermore, the proposed sample size would have >90% power to detect a difference of 10% for change from baseline in actigraph based sleep efficiency, assuming a variability of 11% (alpha=0.05, 2-sided). The variability estimate was based on (8) for actigraphy based sleep efficiency at week 4, inflated by 50% to account for possible increase in variability over time (from week 4 to week 16). Of note, the data used for actigraphy parameters are limited.

Allowing for drop outs, a total of approximately 201 patients will be enrolled in the study.

Considering the uncertainty of the variability of the primary endpoint, when data are available for this endpoint from about 50% of the patients, the variability will be assessed in a blinded manner, and the sample size will be re-estimated. If the re-estimated sample size is higher than the original estimate, the sample size may be increased accordingly, not to exceed a total of 150 additional patients.

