8.2.23. Multiplicity issues

The overall type-I error rate will be controlled at the two-sided 0.05 level using a sequential testing procedure. In order for any secondary endpoints to be eligible for being declared significant, the primary endpoint must be significant at 0.05 significance level. The secondary endpoints will be tested following the hierarchical testing procedure with a pre-specified order, that is, inferential conclusions about successive secondary endpoints require statistical significance at 0.05 significance level of the previous one.

The following key secondary endpoints will be included in the multiplicity adjustment scheme and tested in the following order:

1. Percent change from baseline to Week 12 in peak pruritus NRS
2. Change from baseline to Week 12 in SCORAD total score
3. Change from baseline to Week 12 in SCORAD sleep VAS
4. Change from baseline to Week 12 in PROMIS Sleep Impairment SF8a score
5. Change from baseline to Week 12 in TST based on actigraphy data
6. Change from baseline to Week 12 in SE based on actigraphy data
7. Change from baseline to Week 12 in WASO based on actigraphy data
8. Change from baseline to Week 12 in SOL based on actigraphy data

Each endpoint will be tested at 0.05 (two-sided) level of significance. If at any step the null statistical hypothesis of no treatment difference is not rejected, the endpoints listed after that step will be reported at nominal level, otherwise will be technically eligible for being declared significant. Regardless of eligibility for being declared significant, all endpoints (non-key secondary and exploratory) will be tested at 0.05 (two-sided) level of significance and reported at nominal level.

9. Safety Analysis

All safety results will be summarized separately within the double-blind treatment period and the overall period (combined double-blind and OLE periods), using the Safety analysis set by actual treatment group and overall.

The observation periods include:

- The **pre-treatment** period is defined as the time from the signed informed consent date up to first administration of the IMP.
- The **randomized on-treatment** period is defined as the time from the first administration of the IMP (on Day 1) to the last administration of the IMP prior to Week 12 + 14 days if the patient does

not enter the OLE period, or until prior to the loading dose at Week 12 if the patient enters the OLE period.

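### The stated 90% power for actigraphy TST requires no growth in SD after week 4, which the same paragraph does not assume for sleep efficiency; both calculations refer to week 16, but the endpoint is week 12

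*SAP*

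**What the plan says.** SAP 4.1 and Protocol 9.2 carry the same paragraph on the actigraphy endpoints. It refers both calculations to phase 2 nemolizumab data at week 4.

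- **TST.** "For TST, to detect a 30 minutes difference between treatments", with "2:1 allocation ratio; alpha=0.05, 2-sided". The SD is the week-4 value carried forward unchanged, and the power is given on that basis: "assuming the same variability at week 16 weeks as seen for Nemolizumab at week 4 (=56 min), then 167 subjects are needed to provide 90%".
- **SE.** A difference of 10% is stated to have more than 90% power, "assuming a variability of 11"%. That SD is the week-4 estimate "inflated by 50% to account for possible increase in variability over time (from week 4 to week 16").
- **Caveat.** The paragraph ends by noting that the actigraphy data are limited.

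SAP 3.1 sets a target of at least 150 evaluable patients (100 dupilumab, 50 placebo) completing to week 12. SAP 4.1 allows for 20% dropout and enrols about 201. The blinded sample size re-estimation in the same section looks only at the variability of the primary endpoint.

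In SAP 8.2.23 the fifth key secondary endpoint is "Change from baseline to Week 12 in TST based on actigraphy data". SE, WASO and SOL follow it in the fixed sequence.

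**The concern.** Two endpoints from the same recordings, referred to the same external data and extrapolated over the same interval, get opposite assumptions about how the SD changes with time. Neither document gives a reason. The choice matters for one endpoint and not for the other: SE keeps more than 99.9% power at its inflated SD, whereas the 90% for TST is reached only if nothing is added.

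The time point is also wrong for this trial. Table 3.1.1 of the SAP and Section 3 of the protocol define both endpoints at week 12. Placebo patients switch to dupilumab at week 12, so there is no placebo comparison at week 16.

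The risk lies in interpretation. TST must be significant before SE, WASO or SOL can be formally claimed. If TST misses, a reader who takes the 90% at face value will treat the result as a negative finding from a well-powered test.

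**Working it through.** **Inputs.** Difference 30 min, SD 56 min, 2:1 allocation, two-sided alpha 0.05 (SAP 4.1, Protocol 9.2). SE inflation factor 1.5, from the same paragraph. Sample sizes: 167 (stated for TST), 150 (evaluable target, SAP 3.1), and 201 × 0.8 = 160.8, about 161 (enrolled less 20% dropout).

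**Formula.** Two-sample t-test. The noncentrality parameter is δ / (SD × √(1/n₁ + 1/n₂)), and power comes from the noncentral t with n₁ + n₂ − 2 degrees of freedom.

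**Step 1: reproduce the plan.** With 111:56, the standard error is 56 × √(1/111 + 1/56) = 9.18. The noncentrality is 30 / 9.18 = 3.27 and power is 90.1%. The smallest total reaching 90% at exact 2:1 is 167. The stated figure reproduces.

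**Step 2: SD scenarios.**

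- No growth: SD 56 min.
- Growth of 50% from week 4 to week 16, prorated linearly to week 12. Eight of the twelve weeks have passed, so growth is 50% × 8/12 = 33.3% and SD = 56 × 1.333 = 74.7 min. The linear proration is an assumption.
- Full 50%: SD = 56 × 1.5 = 84 min. This applies a week-16 factor in full at week 12, so it is an upper bound.

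**Step 3: power at the planned sizes.**

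| SD (min) | N=167 (111:56) | N=161 (107:54) | N=150 (100:50) |
|---|---|---|---|
| 56 | 90.1% | 89.1% | 86.7% |
| 74.7 | 68.3% | 66.7% | 63.5% |
| 84 | 58.2% | 56.6% | 53.5% |

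Even with no growth, power is a little under 90% at 161 and at 150.

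**Step 4: alternative reading of the inflation.** The plan labels its primary-endpoint variability as a standard deviation, so the 50% is read here as applying to the SD. If it meant the variance, SD = 56 × √1.5 = 68.6 min and power at N=167 is 75.6%.

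**Step 5: SE for comparison.** Difference 10, SD 11, 100:50 gives 99.9% power. The pre-inflation SD is 11 / 1.5 = 7.3%. Inflating it costs SE nothing that matters.

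**Step 6: link to enrolment.** 167 × 1.2 = 200.4, and the next multiple of 3 is 201. The enrolled number therefore appears to derive from the TST figure, though neither document says so.

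**The case against.** The strongest reply is that the plan states its TST assumption openly, gets the arithmetic right on it, and warns that the data are limited. The trial is sized on the primary endpoint, and this sentence changes no test or estimate. All of that stands. What it does not supply is a reason for treating TST and SE differently, or for using week 16.

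Several stronger readings are tempting, and the documents do not support them.

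- **That 167 for 90% is a calculation error.** It is not; it reproduces.
- **That the real TST power is 58%.** This needs the full week-16 inflation at week 12 and a factor that the plan states only for SE, and only as a possibility. Nor does the fact that TST is the numerator of SE imply 1.5, because TST also varies with time in bed. As an illustration outside the documents, take 7 to 9 hours in bed and independent contributions. The SE part of the TST SD is 7.3% × 420 to 540 min, about 31 to 40 min. Inflating only that part by 1.5 gives a TST SD of about 66 to 71 min and power of about 79% to 72% at N=167.
- **That the primary endpoint's inflation of about 20% is a precedent.** It covers a change of instrument, from the SCORAD sleep VAS to the NRS, not growth over time.
- **That the external study used the same actigraphy device.** The documents do not say.
- **That SE should be tested before TST.** Protocol 8.1.4 leaves the order to the SAP, and the listing order in Protocol Section 3 carries no testing meaning. SE's very high power also rests on a generous 10-point difference. Order is a preference, not a correction.

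Finally, the planned analysis is a baseline-adjusted MMRM, while these figures come from an unadjusted t-test. The stated 167 reproduces with that t-test, so the comparison is like for like.

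**Conclusion.** The inconsistency is real, and it is one of assumption rather than arithmetic. The 90% for TST holds only if the SD stays at its week-4 value of 56 min, and the paragraph does not grant that to SE over the same interval. Power at N=167 runs from 90% (no growth) through about 68% (prorated 50%) to about 58% (upper bound). At the 150 evaluable target the range is 87%, 63% and 54%.

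These are scenarios, not forecasts. They rest on reading the inflation as applying to the SD, on linear proration for the middle case, and on borrowing the SE factor. The actual growth in the TST SD is not documented, and the blinded re-estimation will not check it.

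A non-significant TST result, which would also close formal testing of SE, WASO and SOL, should not be read as coming from a test with assured 90% power. The point touches neither the primary endpoint's power nor type I error control.

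**What to change.** In SAP 4.1 and Protocol 9.2:

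1. Change week 16 to week 12 in both actigraphy calculations.
2. Replace the single TST figure with a conditional statement, for example: for a 30 min difference in TST at week 12 (2:1, two-sided 0.05), an SD of 56 min gives 90% power at 167 evaluable patients, 89% at 161 and 87% at 150; an SD of about 75 min gives about 68% at 167 and 63% at 150; an SD of 84 min, taken as an upper bound, gives about 58% at 167 and 54% at 150. State that the growth in the SD is not known.
3. If there is a reason to hold the TST SD fixed while inflating that of SE, give it.
4. Add a sentence that TST precedes SE, WASO and SOL in the sequence of SAP 8.2.23, and that a non-significant result is to be interpreted against this range.

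The cost is text only: no extra patients, no change to the testing order, and no change to any analysis. The stated TST power becomes less favourable. The SAP can be revised before database lock. A protocol change requires an amendment with IRB/IEC approval (Protocol 10.1.1). If that is out of proportion, the corrected statement can go in SAP 4.1 and be recorded among the changes from the protocol in SAP Section 13.

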4.2. Randomization, Stratification, and Blinding

Randomization will be stratified by: PSG (regardless of geographic location), non-PSG US, non-PSG Europe and non-PSG rest of world (ROW).

A participant who has been allocated to a randomized intervention regardless whether the intervention kit was used or not (ie, participant registered by the interactive response technology (IRT) will be considered a randomized subject). A participant cannot be randomized more than once in the study.

4.3. Analysis Sets

Patients exposed to IMP before or without being randomized will not be considered randomized and will not be included in any analysis set and will be reported in listings under a treatment group named “not randomized but treated”. However, if these patients experienced any safety event, they would be documented separately in the clinical study report.

Patients randomized but not treated will be included in any efficacy analyses and will be reported in listings under a treatment group named “randomized but not treated”. These patients will be analyzed for efficacy analyses according to the treatment group to which they are allocated to by the IRT.

4.3.1. Screened Analysis Set

The Screened analysis set includes all participants who sign the informed consent form (ICF).

4.3.2. Intent-to-Treat (ITT) Analysis Set

The Intent-to-Treat analysis set (ITT) consists of randomized patients (patients with a treatment kit number allocated and recorded in the IRT database, regardless of whether the treatment kit was used or not).

4.3.3. Modified ITT (mITT) Analysis Set

The modified ITT analysis set (mITT) consists of ITT patients who had a baseline and at least one post-baseline measurement.

4.3.4. OLE Analysis Set

The Open-Label Extension (OLE) analysis set consists of ITT patients who completed the double-blind treatment, entered the open label extension period and took at least one dose during the OLE period.

4.3.5. PSG Analysis Set

The PSG analysis set consists of ITT patients who participated in the PSG sub-study and have both baseline and at least one post-baseline PSG assessment.

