10.10 APPENDIX 10: POLYSOMNOGRAPHY (PSG) SUB-STUDY

1. Introduction

Patients with AD are known to have significant sleep disorders due to scratching and perhaps other AD related pathophysiology. The overall objective of the current study is to evaluate the sleep quality of these AD patients treated with dupilumab, using sleep diary and actigraphy, and other patient reported assessments.

Within this study a PSG sub-study is planned for approximately 30 patients.

Polysomnography is a multi-parametric test used in the study of sleep (eg, biophysiological changes that occur during sleep) and it is a standard diagnostic tool in sleep medicine.

Polysomnography is typically performed at night, usually in a clinic. Sleep parameters that are commonly obtained during a PSG procedure will be collected for this study, mainly including sleep onset latency (SOL), wake after sleep onset (WASO), total sleep time (TST), longest sleep episode, stages of sleep, sleep efficiency and arousal index.

The objective of the PSG sub-study is to evaluate the above sleep parameters with a more objective assessment tool to provide additional robust data in support of the diary and actigraphy evaluations.

2. Patients

Of the 201 participants, approximately 30 consenting patients (approximately 20 dupilumab and 10 placebo patients) will participate in this PSG sub-study.

Based on expert input, review of the limited literature and operational feasibility it is decided that a sample size of 30 patients could be sufficient to gather reliable PSG data to represent the whole study group. The PSG data from this group will not be used in statistical comparisons between dupilumab and placebo therefore no statistical considerations took place in deciding the subgroup size. Centers selected for the PSG sub-study are experts in sleep research and have ample experience with regard to PSG procedures and data collection/scoring. Selection of patients for the PSG sub-study will be based on proximity (where patients live) to participating sleep centers and availability for several overnight stays at the centers per study protocol.

3. Schedule

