PSG sub-study: of the 201 participants, approximately 30 patients total (approximately 20 dupilumab and 10 placebo patients) will participate in a PSG sub-study at selected US sites. Each patient who participates this sub-study will have a total of 3 overnight PSGs: at baseline timepoint, 2 (preferably) consecutive overnight PSGs to control for “first night effect” (night of Day -2) and collect baseline data (night of Day -1; which will serve as baseline assessments); then 1 overnight PSG at Week 12. Selection of patients for the PSG sub-study will be based on their proximity to participating sleep centers and availability for overnight stay.

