4.4.6. Baseline, study day and duration derivations

The baseline value of efficacy parameters is defined as the last available valid (non-missing) value on or prior to randomization and prior to the first dose of study medication except as noted below.

- For assessments to be completed daily during the week prior to baseline visit (e.g., sleep NRS, actigraphy parameters, sleep diary, etc.), their baseline value will be the average of 7 continuous - days of assessments (or at least 5 days if data for 7 days were not available) prior to the Visit 1 Week 0 baseline visit but after the Screening visit.
- Polysomnographic data collected at the acclimation night (Day -2) will not be used.

The baseline value of safety parameters is defined as the last available valid (non-missing) value prior to the first dose of investigational medicinal product (IMP).

If multiple valid values of a variable (efficacy or safety) exist within a same day and time is not available, the scheduled value will be used. If no scheduled value is available, then the average will be selected.

Baseline safety and efficacy results are presented in the safety and efficacy analyses.

The reference day (denoted as Day 1) for the calculation of extent of exposure and study day for AE listings will be the day of the first administration of IMP:

- Extent of exposure (see [Section 7.2.1](#))
- Study day for AE listing: AE onset date – first administration date of IMP + 1

The reference day (denoted as Day 1) for the calculation of study day of efficacy assessments will be the randomization date.

- For visit prior to randomization, study day = assessment date – randomization date.
- For visit at or after randomization, study day = assessment date – randomization date + 1.

Intervals that are presented in weeks will be transformed from days to weeks by using (without rounding) the following conversion formula:

$$\text{WEEKS} = \text{DAYS} / 7$$

Intervals that are presented in months will be transformed from days to months by using (without rounding) the following conversion formula:

$$\text{MONTHS} = \text{DAYS} / 30.4375$$

The last on-treatment value of safety parameters is the final measurement assessed during the treatment epoch (double-blind treatment period and OLE period respectively), regardless of the introduction of rescue therapy, including measurements at unscheduled visits.

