- Group 4: Sleep quality NRS versus PVT variables, ANAM variables, WPAI-AD variables and days missed from school or from work.
- Group 5: Sleep quality NRS versus PVT variables, ANAM variables, WPAI-AD variables and days missed from school or from work for Week 24, and Change from baseline to Week 24

For actigraphy and sleep diary data, the weekly averages will be used for correlations. Additionally, for Group 3, the same day assessment (not the average) will be used.

Additionally, relationship between PSG and actigraphy data for the PSG analysis set will be analyzed by providing scatter plots for each of the PSG parameters versus the corresponding actigraphy parameters. For actigraphy data, the same day assessment (not the average) as those of the PSG data will be used.

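### Two exclusions meant for the PSG efficacy baseline also leave at least a third of same-night PSG/actigraphy pairs out of the exploratory device comparison

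*SAP*

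**What the plan says.** SAP 3.1 plans that "approximately 30 patients total (approximately 20 dupilumab and 10 placebo patients) will participate in a PSG sub-study" and that each of them "will have a total of 3 overnight PSGs": an acclimation night (Day -2), a baseline night (Day -1) and one night at Week 12. SAP 4.3.5 defines the PSG analysis set as "ITT patients who participated in the PSG sub-study and have both baseline and at least one post-baseline PSG assessment", and Week 12 is the only planned post-baseline PSG. SAP 4.4.6, in a bullet under the baseline definition, states: "Polysomnographic data collected at the acclimation night (Day -2) will not be used".

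SAP 8.2.22 then compares the devices in two ways.

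- **Scatter plots.** The "relationship between PSG and actigraphy data for the PSG analysis set will be analyzed by providing scatter plots", using actigraphy from the same day as the PSG.
- **Group 3 correlations.** PSG is correlated with actigraphy and with the sleep diary at baseline, at Week 12 and for the change, using weekly averages and also same-day values. The population is described only as the patients in the sub-study, without naming the PSG analysis set.

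The summary table in SAP 15.1 lists mITT for the correlations between sleep and AD measures and has no separate row for PSG against actigraphy.

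Paired data should exist on all three nights. Protocol Appendix 10 has patients arrive at the sleep centre wearing the actigraph, and footnote d of the schedule of activities keeps actigraphy and diary running through Day -1 for sub-study patients. The same appendix says the sub-study is meant to "provide additional robust data in support of the diary and actigraphy evaluations".

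**The concern.** A set that requires a post-baseline PSG is right for change from baseline. A comparison of two devices on the baseline night needs only that night. A patient with good baseline recordings who has no Week 12 PSG therefore drops out of the baseline scatter plots for a reason unrelated to the comparison.

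The Day -2 rule is similar. The first-night effect is a good reason not to use that night as the efficacy baseline. It is not a reason to leave the night out of a same-night comparison, because both devices record the same disturbed sleep.

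What is at stake is precision in a small sub-study. The protocol rules out treatment comparisons on PSG, so the match with actigraphy is one of the main ways these recordings can support the actigraphy results.

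**Working it through.** **Inputs.** N = 30 patients and three PSG nights each (SAP 3.1). No PSG-specific dropout rate is given. SAP 4.1 gives a whole-trial allowance: "Allowing for 20% dropouts, a total of approximately 201 patients will be enrolled in the study". That total reproduces as 167 × 1.20 = 200.4, rounded up to 201, where 167 is the SAP's own figure for total sleep time. The 20% is therefore a planning allowance for the trial and is only an assumption here. I also assume that every PSG night has a valid actigraphy record.

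**Formula.** Let d be the proportion of sub-study patients with no Week 12 PSG.

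- Pairs collected = N + N + N(1−d) = N(3−d)
- Pairs used on the PSG analysis set without Day -2 = 2N(1−d)
- Unused share = 1 − 2(1−d)/(3−d) = (1+d)/(3−d), whatever N is

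**At N = 30 and d = 20%.** Collected: 30 + 30 + 24 = 84. Used: 24 + 24 = 48. Unused: 36, and 36/84 = 42.9%. Of the 36, 30 are Day -2 nights (30/84 = 35.7%) and 6 are Day -1 nights of patients without a Week 12 PSG (6/84 = 7.1%).

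**Range over d.** If instead all sub-study patients count and only Day -2 is left out, the unused share is N/[N(3−d)] = 1/(3−d).

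| d | PSG analysis set: (1+d)/(3−d) | All sub-study patients: 1/(3−d) |
|---|---|---|
| 0% | 33.3% | 33.3% |
| 10% | 37.9% | 34.5% |
| 16.9% (201 to 167) | 41.3% | 35.3% |
| 20% | 42.9% | 35.7% |
| 25.4% (201 to 150) | 45.7% | 36.4% |
| 30% | 48.1% | 37.0% |

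**Effect on precision in the baseline period.** This is illustrative. Assume a true correlation of 0.6 and a within-patient correlation of 0.5 between the two baseline nights. The effective number of pairs from 60 nights is then 60/(1 + 0.5) = 40. The Fisher-z interval is tanh[atanh(0.6) ± 1.96/√(n−3)], with atanh(0.6) = 0.693.

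- n = 24 (PSG analysis set at d = 20%): 0.693 ± 0.428, or 0.26 to 0.81, width 0.55
- n = 30 (all sub-study patients, Day -1 only): 0.693 ± 0.377, or 0.31 to 0.79, width 0.48
- effective n = 40 (both baseline nights): 0.693 ± 0.322, or 0.35 to 0.77, width 0.41

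The unrounded widths are 0.548, 0.484 and 0.413. The narrowing is 1 − 0.413/0.548 = 25% from n = 24, and 1 − 0.413/0.484 = 15% from n = 30.

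The effective-n formula is the design effect for a mean, and the SAP specifies Spearman coefficients with p-values for PSG data, so these intervals are only approximate.

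**The case against.** The strongest reply is that leaving out Day -2 is deliberate. The protocol plans that night to absorb the first-night effect, the SAP calls it the acclimation night, and the sentence sits among exceptions to the baseline definition, so it may cover the baseline value only. That reading is possible. But the wording is unqualified and no planned correlation has a Day -2 time point, so a programmer would probably leave the night out everywhere. The reply does settle that the exclusion should stay for the efficacy baseline.

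Second, the PSG analysis set is named only for the scatter plots, which carry no confidence interval. If Group 3 takes all sub-study patients, someone with a baseline pair and no Week 12 PSG stays in the baseline correlation, and the 15% figure applies. This stands, and the unclear population is itself worth correcting.

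Third, losses to the set rule could be below 20%. Patients who stop treatment are encouraged to stay in follow-up, and the PSG analysis window in SAP 15.5 accepts any post-baseline recording. This also stands, so 43% should not be read as a property of the design.

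A reader might infer that the key secondary actigraphy endpoints (numbers 5 to 8 in SAP 8.2.23) are weakened. The documents do not support that: no test, estimate or gatekeeping step for them uses the PSG/actigraphy relationship, the sub-study size had no statistical basis, and PSG endpoints are not formally tested.

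**Conclusion.** The point holds as a modest, avoidable loss of precision in exploratory agreement analyses. If Day -2 is left out, one third of the same-night pairs go unused even with complete follow-up. The share reaches about 43% only for analyses on the PSG analysis set and only if 20% of sub-study patients have no Week 12 PSG. If Group 3 takes all sub-study patients, it is about 36% at the same d. The Day -2 sentence accounts for 30 of the 36 lost pairs, so the set definition is the smaller part.

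The 15% to 25% gain in interval width rests on an assumed correlation of 0.6 and an assumed within-patient correlation of 0.5, neither of which is in the documents. It would be nice to have and changes no confirmatory conclusion.

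**What to change.** Keep the PSG analysis set and the Day -2 exclusion for the PSG baseline and change-from-baseline summaries, and say in SAP 4.4.6 that the exclusion applies to those.

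In SAP 8.2.22, define one population for the Group 3 same-day correlations and the scatter plots: every ITT patient-night with a valid PSG and a valid same-night actigraphy (or diary) record, whether or not the patient has a Week 12 PSG. Include Day -2 nights, mark them separately, and show results without them as well. Align SAP 15.1 by adding a row for these comparisons. Where nights are pooled, use patient-clustered intervals, for example by bootstrapping patients.

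The cost is a few SAP sentences and slightly more programming. Nights within a patient are correlated, which is why the clustered interval is needed. No new data are required.
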